# PHASE IV TRIAL TO USE STEREOTACTIC BODY RADIOSURGERY (SBRT) FOR BENIGN AND MALIGNANT HEAD AND NECK TUMORS

## SCHEMA

R	Stereotactic Body Radiotherapy (SBRT)
E	Benign Head and Neck Tumors: Paranglioma
G	Chordoma
	Chondrosarcoma
I	Suggested Dose-Fractionation: 14-16 Gy / 1 fraction
S	18-21 Gy / 3 fractions (6-7 Gy per fraction)
	25-45 Gy / 5 fractions (5-9 Gy per fraction)
T	Malignant Head and Neck Tumors: Nasopharynx Cancer
E	Unresectable Cancers
R	Suggested Dose-Fractionation: 8-12 Gy / 1 fraction
	12-18 Gy / 3 fractions (4-6 Gy per fraction)
	35-45 Gy / 5 fractions (7-9 Gy per fraction)

### Chemotherapy

Chemotherapy may be given at the discretion of the patient's medical oncologist. However, ideally chemotherapy, including immune-modifying drugs, should not have been given within 2 weeks of starting radiation and should not resume until at least 2 weeks after completing radiation.

### Eligibility

- Patient age  $\geq$  18 years
- Zubrod performance status of 0-3
- Benign head and neck tumors such as paraganglioma (ex. Glomus jugulare, glomus tympanicum, carotid body tumors), chordoma, chondrosarcoma, angiofibroma
- Malignant head and neck cancers such as invasive squamous cell carcinoma, adenocarcinoma, nasopharyngeal carcinoma, salivary gland cancers, and sarcomas
- No pregnant or lactating women (negative pregnancy test for women of child-bearing age)
- Signed study-specific consent form

## **1.0 Introduction**

Stereotactic Body Radiotherapy (SBRT) is a novel technique in the radiation oncology community. SBRT has evolved as a treatment option for malignant skull base lesions, and can be used to treat recurrent head and neck cancers (1-6).

Nasopharynx cancer has been treated effectively with radiation therapy. Due to recent advances in radiation oncology and the combined use of chemotherapy, improvements in local control and overall survival have been obtained over the last decade. Local recurrence still occurs and generally the outcome for salvage treatment has been poor. Due to the anatomical location of the nasopharynx, recurrent nasopharynx cancer is difficult to treat. SBRT has been used successfully to treat recurrent disease (3-6). In addition to recurrent disease, SBRT has been used successfully as a boost after external beam radiation to safely increase the radiation dose to tumors (7,8).

For patients with locally recurrent head and neck cancer arising from the oral cavity, oropharynx, larynx, or hypopharynx treatment options may be limited. For patients who have received prior radiation therapy, additional standard external beam radiation therapy may not be an option. For patients who develop recurrence at the skull base, complete surgical resection usually can not be achieved. Patients may experience symptoms which can diminish their quality of life. Pain is a common symptom of recurrent head and neck cancer. Stereotactic body radiotherapy may provide excellent palliation for patients with recurrent head and neck cancers. Most patients who receive SBRT have excellent palliation of pain. In addition, some patients may achieve long term local control (9-11).

Chordomas are locally aggressive and destructive tumors with high recurrence rates. Chondrosarcomas arise from the skull base and tend to affect lower cranial nerves. Complete surgical resection is rarely feasible for these lesions. Various modalities of fractionated radiation therapy have been used to increase local control. Stereotactic body radiotherapy delivers more conformal radiation with greater radiobiological effect than conventional radiation therapy. Compared to conventional radiation therapy, SBRT may reduce toxicity to normal surrounding structures and potentially cause fewer complications. Martin et al. from the University of Pittsburgh reported on 28 patients treated with SBRT as a boost after external beam radiation or as the sole treatment. The median follow up was 7 years. The five year local control rate for chondrosarcomas was 80%. The five year local control rate for chordomas was 62%. One patient developed mild dizziness and nausea which was controlled with a two week course of corticosteroids. No long term side effects were reported. The authors concluded that SBRT is an important treatment option for chordomas and chondrosarcomas(12-15).

## **2.0 Objectives**

This study will evaluate the local control rates as well as acute and late toxicity rates of stereotactic body radiotherapy (SBRT) for the treatment of benign and malignant head and neck tumors.

### **2.1 Hypothesis**

**2.1.1** For selected patients with primary or recurrent head and neck tumors, stereotactic body radiotherapy (SBRT) is technically feasible with acceptable complication rates.

### **2.2 Study Design**

**2.2.1** Single site, non-randomized, prospective, phase IV study

**2.2.2** Composed of 3 patient groups:

- Benign tumors, such as paraganglioma (ex. Glomus jugulare, glomus tympanicum, carotid body tumor) chordoma, chondrosarcoma, as the sole treatment or to gross residual disease after maximal safe resection
- Malignant tumors, such as nasopharynx cancer and squamous cell carcinoma, after initial external beam radiation (Residual Disease Group)
- Unresectable malignant tumors, such as nasopharynx cancer and squamous cell carcinoma, adenocarcinomas, and sarcomas which are recurrent after prior radiation (Primary RT Group)

**2.2.3** Data collected will include baseline patient demographics, pathology data, radiation therapy procedure, tumor recurrence data, and toxicities.

**2.2.4** Follow up data will be collected during the patient's standard office visits. The anticipated duration of this study is 5 years.

### **2.3 End Points**

**2.3.1** Primary endpoints will be local control rate and complication rate

- Local recurrence is defined as cancer recurrence within the target volume.
- Local control rate will be evaluated by imaging techniques, physical exam and biopsy, if applicable.
- Evaluation of complication rates (see Section 9.3 for definitions)

**2.3.2** Secondary endpoint will be overall survival

## **3.0 Patient Selection**

### **3.1 Eligibility Criteria**

**3.1.1** Patient age  $\geq$  18 years

**3.1.2** Zubrod performance status of 0-3

**3.1.3** Benign head and neck tumors such as paragangliomas (ex. Glomus jugulare, glomus tympanicum carotid body tumor), chordoma, chondrosarcoma

**3.1.4** Malignant head and neck cancers such as invasive squamous cell carcinoma, adenocarcinoma, nasopharyngeal carcinoma, salivary gland cancers, and sarcoma

**3.1.5** No pregnant or lactating women (negative pregnancy test for women of child-bearing age)

**3.1.6** Signed study-specific consent form

### **3.2 Exclusion Criteria**

**3.2.2** Pregnant or lactating women, due to potential exposure of the fetus to RT and unknown effects of RT on lactating females

**3.2.3** Patients with psychiatric or addictive disorder that would preclude obtaining informed consent

## **4.0 Pretreatment Evaluation**

- 4.1 Patient history, including prior radiation and chemotherapy treatments
- 4.2 Physical examination with the location and palpable size of the lesion in cm
- 4.3 CT scan of involved head and neck region
- 4.4 Other imaging studies are optional, including PET

## **5.0 Simulation**

- 5.1 Fabrication of a custom mask and bite block immobilization device or placement of a stereotactic head frame
- 5.2 Treatment planning CT scan acquired in treatment position with patient's head immobilized

## **6.0 Radiation Therapy**

### **6.1 Target Definition**

- 6.1.1 Gross tumor volume (GTV) is contoured on the planning CT scan. If available, Diagnostic CT scan, MRI and/or PET images may be utilized to construct the GTV by registering them to the planning CT dataset.
- 6.1.2 At the discretion of the treating radiation oncologist, the GTV margins may be expanded to form the planning target volume (PTV).

### **6.2 Dose-Specification**

- 6.2.1 Radiation beams will conform to the PTV outline without additional margin and the dose will be prescribed to the isodose line (IDL) that covers at least 95% of the PTV, which is typically around 80%.
- 6.2.2 SBRT dose-fractionation scheme will be chosen at the discretion of the treating radiation oncologist, but the normal tissue dose constraints should be maintained. Suggested dose-fractionation schemes, derived from the available literature, are listed below. Also included are the corresponding biologic equivalent dose (BED) for each based on the linear-quadratic model:

	SBRT scheme	BED (<math>\alpha/\beta=10</math>)	BED (<math>\alpha/\beta=3</math>)	Equivalent 2 Gy/Fx Dose (<math>\alpha/\beta=10</math>)	Equivalent 2 Gy/Fx Dose (<math>\alpha/\beta=3</math>)
Paraganglioma	14 Gy x 1	33.6 Gy	79.3	28	47.6
	15 Gy x 1	37.5 Gy	90	31.3	53.9
	16 Gy x 1	41.6 Gy	101	34.7	60.5
	6 Gy x 3	28.8 Gy	54	24	32.4
	7 Gy x 3	35.7 Gy	70	29.9	41.9
	5 Gy x 5	37.5	66.7	31.3	40.0

Chordoma Chondrosarcoma	6 Gy x 5	48	90	40	53.9
	7 Gy x 5	59.5	117	49.6	70
	8 Gy x 5	72	147	60	88
	9 Gy x 5	85.5	180	71.3	108
Malignant Cancer (Residual Disease)	8 Gy x 1	14.4	29.3	12	17.6
	9 Gy x 1	17.1	36	14.3	21.6
	10 Gy x 1	20	43	16.7	25.8
	11 Gy x 1	23.1	51.3	19.3	30.1
	12 Gy x 1	26.4	60	22	35.9
	4 Gy x 3 5 Gy x 3	16.8 22.5	28 40	14 18.8	16.8 23.9
Malignant Cancers (Recurrent)	8 Gy x 1	14.4	29.3	12	17.6
	9 Gy x 1	17.1	36	14.3	21.6
	10 Gy x 1	20	43	16.7	25.8
	11 Gy x 1	23.1	51.3	19.3	30.1
	12 Gy x 1	26.4	60	22	35.9
	13 Gy x 1	29.9	69.3	24.9	41.6
	14 Gy x 1	33.6	79.3	28	47.6
	4 Gy x 3	16.8	28	14	16.8
	5 Gy x 3	22.5	40	18.8	23.9
	6 Gy x 3	28.8	54	24	32.4
	7 Gy x 5	59.5	117	49.6	70
	8 Gy x 5	72	147	60	88
	9 Gy x 5	85.5	180	71.3	108

Cancers are assumed to have an  $\alpha/\beta$  ratio of approximately 10

Normal tissues are assumed to have an  $\alpha/\beta$  ratio of approximately 3

### **6.3 Normal Tissue Dose Constraints**

**6.3.1** Normal tissue dose constraints will depend on whether nearby critical normal tissues have received prior external beam radiation, what dose they received, and the time between prior radiation and the current SBRT treatment course. These dose limits will ultimately be determined by the treatment radiation oncologist. For patients who have received prior radiation therapy, every effort should be taken to limit the cumulative doses to adjacent critical normal tissues as follows based on standard fractionation schemes (1.8-2 Gy per day):

Spinal cord –  $D_{max} = 50$  Gy

Brainstem –  $D_{max} = 60$  Gy

Optic Nerves –  $D_{max} = 50$  Gy

Optic Chiasm -  $D_{max} = 54$  Gy

**6.3.2** For patients in whom SBRT is planned following initial standard-fractionation wide-field external beam radiation (Residual Disease Group), the initial radiation course should be designed to limit exposure to adjacent critical normal tissues as follows:

Spinal cord –  $D_{max} = 40$  Gy

Optic Apparatus –  $D_{\max} = 50$  Gy

Brainstem –  $D_{\max} = 50$  Gy

- 6.3.3** For patients who have not received prior radiation therapy, the following dose limits should be maintained:

Structure	1 Fraction	3 Fractions	5 Fractions
Optic Chiasm	8 Gy $D_{\max}$	12 Gy $D_{\max}$	14 Gy $D_{\max}$
Optic Nerve	8 Gy $D_{\max}$	12 Gy $D_{\max}$	14 Gy $D_{\max}$
Brainstem	14 Gy $D_{\max}$	22 Gy $D_{\max}$	27 Gy $D_{\max}$
Spinal Cord	8 Gy to < 0.5 cc 10 Gy to < 0.3 cc 12 Gy to < 0.15 cc	18 Gy $D_{\max}$	22 Gy $D_{\max}$
Brachial Plexus	14 Gy $D_{\max}$	24 Gy $D_{\max}$	25 Gy $D_{\max}$
Internal Carotid Artery in Cavernous Sinus	25 Gy $D_{\max}$	32 Gy $D_{\max}$	35 Gy $D_{\max}$
Oculomotor Nerves in Cavernous Sinus	30 Gy $D_{\max}$	32 Gy $D_{\max}$	35 Gy $D_{\max}$
Esophagus	15 Gy $D_{\max}$	24 Gy $D_{\max}$	30 Gy $D_{\max}$
Skin	15 Gy $D_{\max}$	24 Gy $D_{\max}$	30 Gy $D_{\max}$

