## **10.2 Minimization of Risks**

Although the risks outlined in Section 9.3 may occur, the likelihood of serious events occurring is considered uncommon as long as certain precautions are taken. The potential risks have been minimized by strict compliance with normal tissue dose constraints as described in Sections 6.3.

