**12.5 Appendix V**

**TREATMENT FORM – Page 1 of 1**

1. Name \_\_\_\_\_ (last) \_\_\_\_\_ (first)

2. RT Number \_\_\_\_\_

3. Tumor Details:

Tumor category:  Benign Head and Neck tumor, specify type \_\_\_\_\_

Malignant Head and Neck Tumor, specify type \_\_\_\_\_

Lesion #	Location	Maximum Diameter (cm)	GTV Volume (cc)	CTV Margin (cm)	PTV Margin (cm)			PTV Volume (cc)
					AP	RL	CC	
1								
2								
3								
4								
5								

4. Treatment Portal Design:

Static gantry angle (coplanar), specify number of fields \_\_\_\_\_

Static gantry angle (non-coplanar), specify number of fields \_\_\_\_\_

Dynamic arc (coplanar), specify number of arcs \_\_\_\_\_

Dynamic arc (non-coplanar), specify number of arcs \_\_\_\_\_

5. Dose-Fractionation Scheme:

Lesion #	Total Dose (Gy)	Dose per Fx (Gy)	# Fx	Prescription IDL (%)	D max (Gy)	BED α/β=10 (Gy)	BED α/β=3 (Gy)	CI
1								
2								
3								
4								
5								

6. Dose to Normal Tissues:

Prior Head and Neck radiation:  No (Table 1)  Yes (Table 2)

Table 1 (No prior Head and Neck radiation)

Normal Tissue	D max (Gy)
Optic Chiasm	
Optic Nerve	
Brainstem	
Spinal Cord	
Brachial Plexus	

Internal Carotid Artery in Cavernous Sinus	
Oculomotor Nerves in Cavernous Sinus	
Esophagus	
Skin	

Table 2 (Prior Head and Neck radiation)

Normal Tissue	D max (Gy)	Prior RT D max (Gy)*	Total D max (Gy) (D max + Prior RT D max )
Optic Chiasm			
Optic Nerve			
Brainstem			
Spinal Cord			
Brachial Plexus			
Internal Carotid Artery in Cavernous Sinus			
Oculomotor Nerves in Cavernous Sinus			
Esophagus			
Skin			

\*Estimation of the dose (Gy) may be required

7. Premedication:

- None
- Anti-nausea, specify drug \_\_\_\_\_, dose \_\_\_\_\_ mg,
- Decadron, specify dose \_\_\_\_\_ mg
- Analgesics, specify drug \_\_\_\_\_, dose \_\_\_\_\_ mg
- Acetaminophen, specify dose \_\_\_\_\_ mg

Person completing form: Signature \_\_\_\_\_ Print Name \_\_\_\_\_

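### The re-irradiation form adds organ doses in raw Gy, but the cumulative limits are on a 1.8-2 Gy per day scale, so the total understates equivalent dose above 2 Gy per SBRT fraction to the organ

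*Protocol*

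**What the plan says.** Section 6.3.1 covers patients with prior radiation. It asks that "every effort should be taken to limit the cumulative doses to adjacent critical normal tissues as follows based on standard fractionation schemes", specifying 1.8-2 Gy per day, and lists Dmax values of 50 Gy for cord, 60 Gy for brainstem, 50 Gy for optic nerves and 54 Gy for chiasm. It leaves the final limits to the treating radiation oncologist.

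Section 6.3.2 covers the Residual Disease Group: "the initial radiation course should be designed to limit exposure to adjacent critical normal tissues as follows", namely cord 40 Gy, brainstem 50 Gy and optic apparatus 50 Gy. The SBRT limits by number of fractions in 6.3.3 open with "For patients who have not received prior radiation therapy, the following dose limits should be maintained", so they do not reach re-irradiated patients.

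Appendix V, item 6, Table 2 is completed when there was prior head and neck radiation. Its last column is headed "Total D max (Gy) (D max + Prior RT D max", a plain sum. The only qualifier, attached to the prior dose, is "Estimation of the dose (Gy) may be required". Item 5 of the same form ("Dose-Fractionation Scheme") records the number of fractions and the BED at α/β of 3, but per lesion and not per organ.

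Section 6.2.2 adopts the linear-quadratic model, and its second footnote begins "Normal tissues are assumed to have an" and gives an α/β of about 3. Section 10.2 states: "The potential risks have been minimized by strict compliance with normal tissue dose constraints as described in Sections 6.3".

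**The concern.** The limits and the recorded total are on different scales. A gray given at 8 Gy per fraction does more to late-reacting tissue than a gray given at 2 Gy per fraction, and 6.2.2 tabulates exactly this for the prescription doses. Nothing in the protocol tells staff to convert the organ dose before adding it to the prior dose.

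At stake is safety in the re-irradiated patients. Section 10.2 rests risk minimization on compliance with 6.3. For these patients the only cumulative figure the form produces can sit at or below the 6.3.1 number while the equivalent dose to cord or brainstem is above it. The exposure is greatest in the Residual Disease Group, for which 6.2.2 suggests only one- and three-fraction schemes. Complication rate is a primary endpoint (2.3.1).

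**Working it through.** **Inputs.** Cumulative limits: cord 50, brainstem 60, chiasm 54 Gy (6.3.1). First-course ceilings: cord 40, brainstem 50, optic apparatus 50 Gy (6.3.2). Linear-quadratic model, α/β = 3 for normal tissue (6.2.2). Form total = SBRT Dmax + prior Dmax (Appendix V, Table 2). Assumed: both maxima at the same point, no recovery between courses, first course at 2 Gy per fraction.

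**Formula.** For organ dose D in n fractions, BED = D(1 + (D/n)/3), and the 2 Gy equivalent is BED/(1 + 2/3) = D(D/n + 3)/5. The raw sum therefore understates by D(D/n + 3)/5 − D = D(D/n − 2)/5. This is zero at 2 Gy per fraction to the organ, positive above and negative below.

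**Reproducing the protocol's figure.** For 10 Gy × 1: 10 × 13/5 = 26.0, against 25.8 in the 6.2.2 table. All 18 distinct schemes in that table reproduce to within 1%, except the 2 Gy equivalent of 11 Gy × 1 (30.1 printed, 30.8 computed). So this is the protocol's own model.

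**Cord and brainstem at the 6.3.2 ceilings (limits 50 and 60).**

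| Organ SBRT Dmax | 2 Gy equivalent | Cord: form / equivalent | Brainstem: form / equivalent |
|---|---|---|---|
| 6 Gy × 1 | 6 × 9/5 = 10.8 | 46 / 50.8 | 56 / 60.8 |
| 8 Gy × 1 | 8 × 11/5 = 17.6 | 48 / 57.6 | 58 / 67.6 |
| 10 Gy × 1 | 10 × 13/5 = 26.0 | 50 / 66.0 | 60 / 76.0 |
| 10 Gy in 3 | 10 × 6.33/5 = 12.67 | 50 / 52.7 | 60 / 62.7 |
| 10 Gy in 5 | 10 × 5/5 = 10.0 | 50 / 50.0 | 60 / 60.0 |

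**Where an excess is hidden.** Both organs have 10 Gy of room. Solving D(D/n + 3)/5 = 10 gives D = 5.73 Gy (n = 1), 8.55 Gy (n = 3) and 10.0 Gy (n = 5). The form total stays within the limit up to D = 10. The hidden window is therefore about 5.7-10 Gy in one fraction, 8.5-10 Gy in three, and empty in five.

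**Optic structures.** The optic nerve has no room at its ceiling (50 against 50), so any added dose shows. The chiasm has 4 Gy: a single 4 Gy reads 54 and equals 50 + 5.6 = 55.6, an excess of 1.6 Gy. In three fractions the equivalent is 53.5, so nothing is hidden.

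**Recurrent disease.** No first-course dose is fixed, so prior cord doses are assumed and the form total is held at 50.
- Prior 45 Gy plus 5 Gy: 53.0 (one fraction), 49.7 (three), 49.0 (five).
- Prior 35 Gy plus 15 Gy: 35 + 15 × 8/5 = 59.0 (three), 35 + 15 × 6/5 = 53.0 (five).

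**Sensitivity, cord 40 Gy plus 10 Gy × 1 (base 66.0).**
- First course at 1.8 Gy per fraction: 40 × 4.8/5 + 26.0 = 64.4.
- α/β from 2 to 4: 70.0 to 63.3. For 10 Gy in three fractions the range is 53.3 to 52.2.
- 40% recovery of the first course: 24 + 26 = 50, which removes the excess.

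**The case against.** The strongest reply is that no governing text is wrong. Section 6.3.1 states its scale correctly, and the Table 2 column is labelled in Gy with its formula, so it is what it claims to be. Table 2 prints no limits, nobody is told to compare its total with 6.3.1, and five of its nine structures have no cumulative limit there. It looks more like data capture than a compliance check. The limits are best-effort, depend on time since the first course, and are finally the oncologist's. The two dose components and the number of SBRT fractions are recorded, so the SBRT part can be converted later.

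The size can also be challenged. A 10 Gy single dose to the cord is 83-125% of the suggested 8-12 Gy Residual Disease prescriptions, and even 5.73 Gy is 48-72% of them. No document shows that organs reach such doses, and 10.4 expects little added dose to nearby tissue. If the maxima do not coincide, the raw sum overstates the true point dose. The suggested schemes are not binding, and the schema lists five-fraction treatment for malignant tumors without excluding the Residual Disease Group.

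All of this stands as a limit on the consequence. It does not make the total comparable with the limits. The form performs one cumulative calculation for re-irradiated patients, on a scale different from that of the only cumulative limits the protocol gives. An oncologist who converts off the form is protected; the protocol does not ask for it.

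**Conclusion.** The point holds and should be corrected. The total in Appendix V, Table 2 cannot be compared with the 6.3.1 limits, and it errs in the unsafe direction whenever the organ receives more than 2 Gy per SBRT fraction. What matters is the organ's dose per fraction, not the prescription's.

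At the 6.3.2 ceilings the hidden excess over the cord or brainstem limit runs from nothing up to 16 Gy in one fraction and 2.7 Gy in three; it is nil in five. The optic structures are little affected. The direction for cord and brainstem at high single-fraction organ doses is stable over α/β from 2 to 4 and over a first course at 1.8 or 2 Gy. The size rests on coincident maxima, no recovery and a prior dose at the ceiling; the protocol gives no patient-level organ doses to test these. The formula permits an excess to pass unnoticed; it does not prescribe one.

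**What to change.** In Appendix V, Table 2, convert SBRT Dmax (with the number of fractions already in item 5) and prior Dmax to 2 Gy equivalents at α/β = 3, and compute the total from the converted values. Keep the raw doses as recorded. Add one sentence to 6.3.1 saying that cumulative totals are summed on that scale.

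The cost is one conversion per structure. A prior course at 1.8-2 Gy per day needs little or none; otherwise its fraction size comes from the radiation history that 4.1 already requires. Where lesions in one patient have different numbers of fractions, the organ dose must be split by lesion before converting. The clinical trade-off is a possibly tighter SBRT dose, and less target coverage, next to previously irradiated organs.

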## **10.4 Justification of the Study**

Patients who have locally recurrent or persistent malignant head and neck cancer after definitive conventionally fractionated radiation therapy pose a therapeutic challenge since complete surgical resection is often not feasible and surrounding critical normal tissues have typically received close to maximum tolerable radiation doses. High dose, precisely targeted radiation with stereotactic body radiotherapy, which delivers minimal additional radiation dose to nearby normal tissues can produce durable local control and palliation of local symptoms such as pain. In addition, some benign head and neck tumors which are located near the skull base and/or involve critical vasculature also pose a surgical challenge. These tumors appear to have a reasonably high local control probability with radiation therapy. SBRT is advantageous in this setting by limiting the dose to adjacent normal tissues in patients who otherwise have a long life expectancy.

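### For an optic nerve or chiasm with a low earlier dose, the cumulative figures in Protocol 6.3.1 can be met with more SBRT dose than 6.3.3 allows a never-irradiated patient

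*Protocol*

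**What the plan says.** Section 6.3 of the Protocol sets normal tissue limits according to radiation history.

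- **6.3.1, prior radiation.** It opens with a general principle: "Normal tissue dose constraints will depend on whether nearby critical normal tissues have received prior external beam radiation, what dose they received", and also the time elapsed. It then says: "These dose limits will ultimately be determined by the treatment radiation oncologist". For these patients "every effort should be taken to limit the cumulative doses to adjacent critical normal tissues as follows based on standard fractionation schemes", and four cumulative maxima follow: spinal cord 50 Gy, brainstem 60 Gy, optic nerves 50 Gy, optic chiasm 54 Gy. The scale is 1.8-2 Gy per day. No separate limit is given for the SBRT course.
- **6.3.3, no prior radiation.** "For patients who have not received prior radiation therapy, the following dose limits should be maintained". For both optic nerve and chiasm the maximum is 8 Gy in 1 fraction, 12 Gy in 3 and 14 Gy in 5.
- **6.2.2.** The scheme is the oncologist's choice, "but the normal tissue dose constraints should be maintained". A footnote to the dose table supplies the conversion parameter: "Normal tissues are assumed to have an" alpha/beta ratio of about 3.
- **Appendix V, Treatment Form.** Patients with no prior head and neck radiation use Table 1 and the others use Table 2. Table 2 adds the SBRT and prior maxima as physical doses, organ by organ.

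**The concern.** An organ that has already received radiation should not have a looser SBRT limit than the same organ in a patient never irradiated. Section 6.3 allows this numerically, because the applicable rule is chosen by the patient's history while the risk depends on the dose the organ received. A patient irradiated well away from the optic pathway moves from 6.3.3 to 6.3.1, where the only optic figure is a cumulative total that is still largely unused.

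Complication rate is a primary endpoint (2.3.1), cranial nerve neuropathy is a listed late event (9.3.3), and 10.2 names adherence to the 6.3 constraints as the means of keeping risk low. A constraint that loosens after prior radiation weakens that safeguard for the patients concerned.

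The Introduction suggests one possible route to such a patient. It describes recurrence of oral cavity, oropharynx, larynx or hypopharynx cancers and adds: "For patients who develop recurrence at the skull base, complete surgical resection usually can not be achieved". It does not say whether the optic structures were spared in such patients.

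**Working it through.** **Inputs.** Cumulative optic figures of 50 Gy (nerve) and 54 Gy (chiasm) from 6.3.1. SBRT optic limits of 8/12/14 Gy in 1/3/5 fractions from 6.3.3. Alpha/beta of 3 and the linear-quadratic model from 6.2.2. The earlier dose to the optic structure is not in the Protocol, so the values below are assumptions, taken at 2 Gy per fraction.

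**Formulas.** For total dose D in n fractions of size d = D/n: BED = D(1 + d/3), and the equivalent dose in 2 Gy fractions is EQD2 = BED/(1 + 2/3) = 0.6 x BED.

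**Step 1: reproduce the Protocol's figures.**
- 8 Gy x 1: BED = 8(1 + 8/3) = 29.3; EQD2 = 17.6 Gy. The 6.2.2 table gives 29.3 and 17.6.
- 4 Gy x 3: BED = 12(1 + 4/3) = 28; EQD2 = 16.8 Gy. The table gives 28 and 16.8.
- 14 Gy in 5 (not in the table): BED = 14(1 + 2.8/3) = 27.1; EQD2 = 16.2 Gy.

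The 6.3.3 optic limits are therefore worth 17.6/16.8/16.2 Gy on the 6.3.1 scale.

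**Step 2: the earlier dose at which the two rules cross.** Crossing = 6.3.1 figure minus EQD2 of the 6.3.3 limit.
- Nerve: 50 - 17.6/16.8/16.2 = 32.4/33.2/33.8 Gy.
- Chiasm: 54 - 17.6/16.8/16.2 = 36.4/37.2/37.8 Gy.

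Below these doses 6.3.1 is looser than 6.3.3; above them it is stricter.

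**Step 3: the SBRT maximum compatible with 6.3.1.** Solve D(1 + D/(3n)) = (6.3.1 figure - earlier dose)/0.6. For the nerve after 20 Gy the right side is 30/0.6 = 50, and for n = 1, D = 1.5 x (-1 + sqrt(1 + 4 x 50/3)) = 10.8 Gy.

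| Structure | Assumed earlier dose | 1 / 3 / 5 fractions (Gy) | Against 8 / 12 / 14 Gy |
|---|---|---|---|
| Nerve | 20 Gy | 10.8 / 17.2 / 20.9 | +35 / +43 / +49% |
| Nerve | 30 Gy | 8.6 / 13.4 / 16.1 | +8 / +12 / +15% |
| Nerve | 35 Gy | 7.3 / 11.2 / 13.3 | below: no inversion |
| Chiasm | 20 Gy | 11.6 / 18.5 / 22.6 | +45 / +54 / +61% |
| Chiasm | 30 Gy | 9.6 / 15.0 / 18.1 | +19 / +25 / +29% |
| Chiasm | 40 Gy | 7.0 / 10.7 / 12.7 | below: no inversion |

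**Step 4: sensitivity.** Over alpha/beta 2 to 4 the crossing runs from 30 to 34 Gy (nerve) and 34 to 38 Gy (chiasm). For the nerve after 20 Gy, the dose compatible with 6.3.1 is 10.0/16.2/20.0 Gy at alpha/beta 2 and 11.6/18.0/21.6 Gy at 4. If physical doses are simply added, as in Appendix V Table 2, the crossings are 50 - 8/12/14 = 42/38/36 Gy (nerve) and 54 - 8/12/14 = 46/42/40 Gy (chiasm). That sum does not match the standard-fractionation scale of 6.3.1, but 6.3.1 does not say how doses are to be combined. The direction is the same either way.

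**Step 5: a residual-disease patient at the 6.3.2 optic maximum of 50 Gy.** The nerve has 50 - 50 = 0 Gy left and the chiasm 54 - 50 = 4 Gy EQD2, which is 3.2/4.5/5.0 Gy in 1/3/5 fractions. Both are well under 8/12/14 Gy, so there is no inversion.

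**The case against.** The strongest reply is that 6.3.1 grants no allowance. Its opening ties the constraint to the dose the organ itself received, its figures are an effort-based ceiling, and the final limit belongs to the oncologist, who may apply 6.3.3 to a spared optic nerve. Table 2 of the form would make a low earlier optic dose visible. All of this stands and reduces the practical reach. It does not alter the fact that the only optic figures given for these patients are the looser ones when the earlier dose is low.

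Second, 10.4 says of recurrent or persistent disease that "surrounding critical normal tissues have typically received close to maximum tolerable radiation doses". In that situation 6.3.1 is already the stricter rule. This also stands. The larger excesses need an assumed earlier dose near 20 Gy; at 30 Gy the nerve excess is 0.6 to 2.1 Gy.

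Third, a looser optic limit could be a deliberate trade-off in unresectable recurrence, set against benign tumors with long life expectancy. That is possible, but the Protocol does not state it, and 6.3 divides patients by radiation history and not by diagnosis.

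A reader might infer that brainstem and spinal cord have the same defect. The figures are too weak to support that. At alpha/beta 3 the brainstem crossing is only 12.4-14.6 Gy, and it moves between 4 and 18 Gy over alpha/beta 2 to 4; after 10 Gy the excess is 3-6%. The cord crossing is 14.0-17.6 Gy, and its one-fraction comparison sets a maximum dose against a volume limit.

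**Conclusion.** The point holds for the optic nerves and chiasm, as a minor one. Below about 32-34 Gy (nerve) or 36-38 Gy (chiasm) of earlier dose, the 6.3.1 figures can be met with more SBRT than 6.3.3 allows a never-irradiated patient, and nothing in 6.3 carries the 6.3.3 optic limits over. These thresholds rest on the Protocol's alpha/beta of 3, the linear-quadratic sum and 2 Gy fractions for the earlier course. The direction survives the alternatives in Step 4. The size of the excess depends wholly on an earlier dose that the Protocol does not give.

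A reader might go further and infer that the Protocol directs higher optic doses in re-irradiated patients, or that the complication rate will be raised. The documents support neither. 6.3.1 asks for doses to be limited and leaves the final figure to clinical judgment. No affected patient can be identified from the text, and the number of such patients is unknown.

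**What to change.** Add one sentence to 6.3.1: *For the optic nerves and optic chiasm, the SBRT course should also stay within the 6.3.3 limits; the stricter of 6.3.1 and 6.3.3 applies.* The word *should* matches the force of 6.3.3 and leaves the discretion clause intact. The SBRT share for an optic structure would then be at most 17.6/16.8/16.2 Gy EQD2, and this ceiling works however the earlier and new doses are summed. The other structures stay as they are.

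The cost is one sentence in an amendment, with no added patients, visits or procedures. The downside is confined to plans beside a previously spared optic structure. Prescribed at roughly the 80% isodose, the recurrent-disease schemes have plan maxima of about 8/0.8 to 14/0.8 = 10-17.5 Gy (1 fraction), 12/0.8 to 18/0.8 = 15-22.5 Gy (3) and 35/0.8 to 45/0.8 = 44-56 Gy (5). A target touching such a structure may therefore lose some coverage on that side, and local control is also a primary endpoint. Above the crossing dose nothing changes.
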